## TITLE COLLAPSIBLE PESSARY FEASIBILITY TRIAL STATISTICAL ANALYSIS PLAN

## 7.0 ADVERSE EVENTS (PRIMARY)

7.1 Endpoint

7.1.1 Prevalence and severity of adverse events, as defined below, that subjects experience using the study pessary.

7.2 Data collection method

7.2.1 At each visit, subjects will report discomfort, displacement, discharge, bleeding, obstructed urination, constipation, and other potential adverse events. If present, each reported event is described subjectively as mild, moderate, or severe by the subject.

7.2.2 At each in-person visit, practitioners will assess for physical exam findings of perineal tearing, vaginal irritation, vaginal ecchymosis, vaginal abrasions/superficial cuts, deep vaginal erosion, vaginal bleeding, granulation tissue, and copious vaginal discharge.

7.2.3 At each additional visit or phone call, expected and unexpected adverse events are reported by patients and/or observed by practitioners.

7.2.4 Study personnel can make entries in their site-specific F-3010 Trial Adverse Event Log for events described above or unique events not otherwise captured.

7.2.5 The events above will be reviewed and adapted to conform to Common Terminology Criteria for Adverse Events (CTCAE) ratings. The CTCAE ratings will be determined by the PI at each site.

7.2.6 The events will be condensed to unique adverse events consisting of:

- New subjective reports of events related to the study pessary not present at baseline with the current pessary
- Worsening subjective reports of events related to the study pessary that were present at baseline with the current pessary
- New physical exam findings related to the study pessary not present at baseline with the current pessary
- Worsening physical exam findings related to the study pessary that were present at baseline with the current pessary
- Any additional entries in the F-3010 Trial Adverse Event Log

These unique adverse events will represent the data analysis set.

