Visit 1 [research purposes] will aim to be scheduled between 3 and 5 weeks from Visit 0 (the conclusion of the washout period). Demographic and historical data will be extracted from the Electronic Medical Record (EMR) if not completed at Visit 0 and supplemented by the subject as needed. Global subject satisfaction of the current pessary will be assessed using a Visual Analog Scale (VAS) with a 10 cm linear continuum in which 0 represents no satisfaction and 10 represents complete satisfaction. As in Visit 0, the current pessary will be observed in situ for the presence of rotation and its ability to support prolapse by measuring the distance of the most dependent compartment of the subject's prolapse to the hymen (points Ba and Bp), as well as the distance from the leading edge of the current pessary to the hymen. The current pessary will be removed, washed, placed in a sealed bag, labeled and either stored or given to the subject for them to return with at their final visit. The physical exam will be repeated as in Visit 0, and the presence of perineal disruption associated current pessary removal will be noted. The appropriate study pessary size for the subject based on the provided mapping from the subject's current pessary and practitioner's expertise will be selected at random from the inventory of study pessaries, removed from its sealed bag, and the study pessary's serial number (labeled on the bag) will be recorded. The subject will be fit with the study pessary. If a study pessary cannot be fit, and the patient is willing, they can be fit with a different sized pessary at Visit 1 or can remain in the study and return for a second attempt to be fit with a study pessary at Visit 2. A VAS will be used to assess the perceived discomfort with removal of the current pessary and, separately, with insertion of the study pessary. For self-managers, ease of current pessary removal and reinsertion will be noted using a VAS and teaching will be provided on the proper technique to insert and remove the study pessary.

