Visit 3 [research purposes] will occur at the conclusion of the 3-month (from Visit 1) treatment phase - a typical length of time between routine visits for patients who choose long term pessary management of their prolapse. It can be scheduled in a window between 11 and 13 weeks from Visit 1. When the subject returns for Visit 3, a physical exam will be repeated, as in previous visits, for comparative data. The study pessary will be observed in situ for the presence of rotation and its ability to support prolapse by measuring the distance of the most dependent compartment of the subject's prolapse to the hymen (Points Ba and Bp), as well as the distance from the leading edge of the study pessary to the hymen. A VAS will be used to assess discomfort with removal of the study pessary, discomfort with reinsertion of their current pessary, and their global satisfaction of the study pessary. The subject will have been instructed to return with their current pessary which was removed in Visit 1. If the subject's current pessary is not brought to the visit, they will be given a new pessary of the size and style of their current pessary. Each subject will complete the PFDI-20, PFIQ-7, and PISQ-R for a post treatment comparison. For self-managers, other data collected will include frequency of removal and a VAS for ease of study pessary insertion and removal.

Additional Visits: Subjects will be seen as necessary and adverse events will be managed according to standard of care. If the study pessary falls out after Visit 1, the subject may be seen at their convenience for reinsertion or resizing. If a study pessary cannot be fit and retained, the subject will be withdrawn from the study and their current pessary will be placed. If the subject's current pessary is not brought to the visit, they will be given a new pessary of the size and style of their current pessary.

Special Circumstances: If a subject dies between Visit 1 and Visit 3, an attempt will be made to contact the coroner to retrieve the study pessary. If the study pessary cannot be retrieved, a copy of the death certificate will be obtained.

The study pessary is the only device that will be used in this trial. There will be no placebo devices placed. The study pessary is not cleared by the FDA, and a rationale is provided for a non-significant risk device claim in the attached documents.

Data Collected

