17.0 Provisions to Monitor the Data to Ensure the Safety of Subjects

Data Analysis and Data Monitoring

This is a non-randomized, non-blinded, feasibility study involving a vaginal pessary. Given that the intervention is known to be safe and well-tolerated and the total exposure to our pessary for each subject was chosen to be similar to the typical interval of continuous pessary use which is common in clinical practice for current pessary users, we don't believe a formal data safety monitoring committee is required. However, a data and safety monitoring plan will be in place. The data safety monitoring plan will focus on low intensity monitoring by the Data Safety Monitoring Team, comprised of the one clinician from each participating site and a biostatistician. The Data Safety Monitoring Team will meet monthly, or sooner if necessary. Their charge will be to review subject accrual,

adherence to study protocol, and monitor adverse events. Additionally, they will ensure prompt reporting of serious adverse events to WCG IRB and the study sponsor (Reia, LLC).

At each contact with the subject, the clinical investigator will seek information on adverse events by specific questioning and by examination. Information on all adverse events will be recorded for review by the Data Safety Monitoring Team. Moderate adverse events which represent a change in baseline from those experienced in the washout period will be reviewed by the Data Safety Monitoring Team within one week. Serious adverse events, as defined by FDA criteria, will be reviewed by the Data Safety Monitoring Team within 24 hours and reported to WCG IRB and the study sponsor (Reia, LLC). Careful monitoring of the recruitment, enrollment, study procedures, and adverse events will help protect the safety of the subjects and quality of the data.

[figure not shown]
Any unanticipated adverse device effects that are possibly, probably, or definitely related to the study intervention will be immediately evaluated by the sponsor, Reia, LLC. If it is determined that the adverse device effect presents an unreasonable risk to the subjects, the investigation will be terminated within 5 working days of making the determination and not more than 15 working days of first receiving notice.

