## TITLE COLLAPSIBLE PESSARY FEASIBILITY TRIAL STATISTICAL ANALYSIS PLAN

**13.0 PROPENSITY & FREQUENCY OF SELF-MANAGEMENT (SECONDARY)**

- 13.1 Endpoint
  - 13.1.1 Change in frequency of pessary removal for self-managers
  - 13.1.2 Change in management style (self-managed or exclusively practitioner-managed)
- 13.2 Data collection method
  - 13.2.1 At visit 0, the subject is asked to estimate the average number times per month their current pessary was removed/reinserted since their last visit.
  - 13.2.2 At visit 1 and visit 3, the subject is asked to estimate the number of times the pessary (current or study) was removed/reinserted since the last visit.
  - 13.2.3 During the visit 2 screen and at visit 2 if it occurs, the subject is asked to estimate the number of times the study pessary was removed/reinserted since visit 1.
- 13.3 Analysis group
  - 13.3.1 Current pessary self-management frequency will be estimated at visit 0 from the subject's memory, while the number self-management events with current pessary between visits will be reported at visit 1. Therefore, only visit 1 data will be used in the frequency analysis of the current pessary.
  - 13.3.2 Since visit 2 occurs 1-3 weeks after visit 1, time between visits is not sufficient to capture self-management. Therefore, visit 2 screen data and visit 2 in-person data will not be included in the frequency analysis. Instead, number of self-management events reported at visit 3, which occurs 11-13 weeks following visit 2, will be used in the analysis of the study pessary.
  - 13.3.3 Since data from visit 3 is required in the frequency analysis, only subjects who complete the study will be included in the analysis group.
  - 13.3.4 Visit 0 and visit 1 data will be used in the management style analysis for the current pessary. Visit 2 and visit 3 data will be used in the management style analysis for the study pessary.
- 13.4 Data analysis plan
  - 13.4.1 For visit 1 and 3 responses, number of self-management events since last visit will be converted to number of self-management events per month (defined as 28 days) using the number of days that passed between visits.
  - 13.4.2 For each subject, a difference (current pessary – study pessary) in number of self-management events per month will be calculated.
  - 13.4.3 A count of subjects who self-manage (number of self-management events per month > 0) will be calculated for the current pessary (visit 0 or 1) and the study pessary (visit 2 or 3).

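### The SAP's one-way count of new or worse events, measured against an undefined baseline, cannot answer the protocol's primary safety comparison between the two pessaries

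*SAP*

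**What the plan says.** Protocol 4.0 lists as a primary endpoint the prevalence and severity of adverse events on the study pessary compared with those on the woman's current pessary. SAP 7.1.1 describes the endpoint for the study pessary only.

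SAP 7.2.6 builds the analysis set from five categories. Two concern new events: "New subjective reports of events related to the study pessary not present at baseline with the current pessary" and "New physical exam findings related to the study pessary not present at baseline with the current pessary". Two are the matching categories for worsening. The fifth admits any additional adverse event log entry and, unlike the other four, does not ask for relatedness. SAP 7.4.1 tallies the set by severity and by type. Section 7 of the SAP does not say which visit or visits form the baseline.

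On timing, Protocol 6.0 says that Visit 1, which ends the washout, "will aim to be scheduled between 3 and 5 weeks from Visit 0". Of Visit 3 it says: "It can be scheduled in a window between 11 and 13 weeks from Visit 1". Current-pessary events are assessed at Visit 0 and again at Visit 1 (Protocol 9.0). Visit 0 takes place at a routine maintenance visit (Protocol 6.0), in women who attend every 3-4 months (Protocol 17.0).

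SAP 7.5.1 defines success as the absence of serious, related events that could put the general population at risk.

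**The concern.** A comparison needs events on both devices, counted in the same way. The SAP's rule runs in one direction. A woman who has an event only on the study pessary is counted, and a woman who has the same event only on the current pessary is not. Events that come and go will therefore give a positive count even if the pessaries are interchangeable. A reader who takes the tally as the answer to the protocol's endpoint would read ordinary variation over time as an effect of the device.

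Observation time makes the tally harder still to read. The study pessary is followed prospectively for longer than the current one, and the tally does not adjust for this. The SAP does adjust elsewhere: 13.4.1 scales self-removal counts to 28-day months using the days between visits.

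**Working it through.** **The plan's own figure.** There is none to reproduce. The documents give no event rate, power or sample size for adverse events. The stated power of .80 concerns the PFDI-20.

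**Inputs from the documents.** Current-pessary washout 3-5 weeks, nominally 4. Study-pessary phase 11-13 weeks from Visit 1, nominally 12. Completers: 40. The window ratio is 12/4 = 3.0, ranging from 11/5 = 2.2 to 13/3 = 4.3. SAP 13.3.2 describes Visit 3 differently, as a visit "which occurs 11-13 weeks following visit 2". Since Visit 2 falls 1-3 weeks after Visit 1, that reading gives 12-16 weeks on the study pessary and a ratio of 12/5 = 2.4 to 16/3 = 5.3.

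**Assumptions.** Identical pessaries; the same constant hazard in all women; risk p of a given event type in 4 weeks set at 5%, 10% or 20%; no relatedness filter.

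**Formulas.** With q = 1 - p, current window a weeks and study window b weeks:

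- counted as new = q^(a/4) × (1 - q^(b/4))
- seen only with the current pessary, not counted = (1 - q^(a/4)) × q^(b/4)

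**Worked case, p = 10%.** Equal 12-week windows: 0.729 × 0.271 = 19.8%. Windows of 4 and 12 weeks: 0.900 × 0.271 = 24.4%, against 0.100 × 0.729 = 7.3% in the other direction.

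Percentage of women per event type, counted as new / seen only with the current pessary:

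| Windows, current / study (weeks) | p = 5% | p = 10% | p = 20% |
|---|---|---|---|
| 12 / 12 | 12.2 / 12.2 | 19.8 / 19.8 | 25.0 / 25.0 |
| 4 / 12 | 13.5 / 4.3 | 24.4 / 7.3 | 39.0 / 10.2 |
| 16 / 12 | 11.6 / 15.9 | 17.8 / 25.1 | 20.0 / 30.2 |

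The last row supposes that Visit 0 captures the 12 weeks before enrolment, which are then added to a 4-week washout.

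**Reading the table.**

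- Equal windows balance the two directions but do not bring the one-way count to zero. Per 40 women at p = 10%, 7.9 would still be counted as new.
- Moving from 12/12 to 4/12 weeks adds 1.3, 4.6 and 14.0 percentage points at the three risks. In each case the larger part of the 4/12 figure is already there with equal windows.
- At p = 10%, the extremes of the permitted windows give 22.1% new (5 and 11 weeks) to 26.8% (3 and 13 weeks).
- If Visit 0 looks back 12 weeks, the imbalance reverses. Per 40 women at p = 10%, 7.1 are counted as new and 10.0 are seen only with the current pessary.

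**Exam-day findings.** Here the number of exams matters more than the length of the window. There are two on the current pessary (Visits 0 and 1) and one or two on the study pessary, because the in-person Visit 2 may be omitted. Assume 10% prevalence at each exam, independent between exams. Two against two gives 0.81 × 0.19 = 15.4% in each direction. Two against one gives 0.81 × 0.10 = 8.1% new and 0.19 × 0.90 = 17.1% seen only with the current pessary.

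**The case against.** The SAP tests nothing here, and its success criterion does not use the count. A list of new or worsened events is a reasonable screen for harm from a new device. Four of the five categories require relatedness to the study pessary, which should remove some background events. All of this stands, and it limits what is at stake. It does not supply the protocol's comparison, however. Relatedness is a weak guard in an unblinded study, and the log-entry category does not require it.

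A reader might infer something stronger: that the shorter washout by itself makes the study pessary look worse, and that the 24% measures this. The documents do not support that reading, for three reasons.

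- Visit 0 also records events and pathology from earlier use of the current pessary, at the end of what may be a routine wear interval. The recall period is not stated in the two documents, and the data collection form is not among them. The direction of the window effect is therefore open.
- Protocol 17.0 does link baseline to the washout: "Moderate adverse events which represent a change in baseline from those experienced in the washout period will be reviewed". But that sentence sets when the monitoring team looks at moderate events. It does not define baseline for the SAP.
- As the table shows, most of the 24% remains when the windows are equal.

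**Conclusion.** The point holds as a mismatch between endpoint and analysis. The protocol promises a comparison, and the SAP's tally cannot deliver it. For identical pessaries the one-way rule yields, per event type, about 12%, 20% and 25% of women counted as new with equal 12-week windows, and 13.5%, 24% and 39% with 4 against 12 weeks, at assumed 4-week risks of 5%, 10% and 20%.

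These sizes rest on assumed rates, a constant hazard and no relatedness filter. They also treat all women as equally prone. If some women are persistently more prone they tend to show the event at baseline, and for the same overall risks the figures would be smaller. The argument is strongest for subject-reported and transient events and weaker for exam findings.

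The unequal windows add to the count if baseline means the washout. Whether they tilt the result for or against the study pessary cannot be settled from the documents. No formal test is invalidated, and the success criterion in SAP 7.5.1 is unaffected. What is affected is the reported tally and any reading of it as a comparison.

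**What to change.** - **SAP 7.4.1:** tabulate all subject-reported events and exam findings for both pessaries under the same definitions. Give subject-reported events per 28 days of observation. Where only presence is recorded, give the proportion of women affected at matched assessments, Visit 0 against Visit 3. Show resolved or improved events beside new or worse ones.
- **SAP 7.2.6:** state which visits form the baseline, and the recall period that applies at each. Taking the worse of Visit 0 and Visit 1 is not a neutral choice. It can set two exams plus earlier wear against a single study-pessary exam, which would favour the device.
- **Raw tally:** keep it, with a statement that it is not a comparison between pessaries.
- **SAP 7.1.1:** reconcile it with the protocol endpoint. Also reconcile the timing of Visit 3 in SAP 13.3.2 with Protocol 6.0, since observation time depends on it.

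The cost is SAP wording and a little more tabulation. Assessments at Visits 0, 1 and 3 are already planned, and 13.4.1 already relies on the days between visits. Rates on the current pessary will be imprecise because its prospective window is short.

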4.0 Study Endpoints

The primary and secondary endpoints of the study are described in the following table:

Type	Name	Time Frame	Brief Description
Primary		the end of washout	The Pelvic Floor Distress Inventory -20 (PFDI-20) is a validated instrument to assess the presence and bother of symptoms that pelvic floor disorders have on health-related quality of life in women. It is a 20-item questionnaire and the short form of the 46 question PFDI. There are three subscales: Urinary Distress Inventory 6 (UDI-6), Colorectal-Anal Distress Inventory 8 (CRADI-8), and the Pelvic Organ Prolapse Distress Inventory 6 (POPDI-6). The overall score range is 0-300. The higher the score, the greater the perceived impact that pelvic floor dysfunction has on a patient's life. The minimal important change in the

D	ΙΛ	DOCUMENT NUMBER	CP-002-01	r 03
K			PAGE	7 of 23

TITLE COLLAPSIBLE PESSARY FEASIBILITY TRIAL PROTOCOL

PAGE 7 OF 23

			PFDI-20 to demonstrate a clinical effect in women choosing conservative management of their prolapse (i.e. a pessary) is between 13.5 and 18.3 points.
Primary	Prevalence and severity of adverse events that subjects experience using the study pessary compared to those experienced with their current pessary	Throughout study [Week 0-16] Adverse events can occur with use of the current pessary or during the treatment phase with the study pessary. They can be experienced with insertion or removal of either the current or study pessary, noted on physical exam, or reported at any time.	Adverse events experienced with insertion or removal of the current or study pessary include: pelvic cramping or discomfort, perineal tear, failure of the study pessary to deploy or collapse, or pessary expulsion. Adverse events noted on physical exam include: vaginal irritation, vaginal ecchymosis, vaginal abrasions/superficial cuts, vaginal erosion, vaginal bleeding, vaginal discharge, or urinary retention. Adverse events which could occur at any time include: pelvic cramping or mild discomfort, copious vaginal discharge, urinary tract infection, substantial discomfort, pessary expulsion (collapsed or deployed), or adverse events unrelated to the pessary or study visit. Each event will be classified as mild (transient and easily tolerated by the subject), moderate (causing discomfort or interrupting usual activities), or severe (causing considerable interference with usual activities, may be incapacitating, or may require hospitalization).

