14.0 Risks to Subjects

This study will involve greater than minimal risk. The subject could experience:

- Discomfort during insertion, use, or removal of the study pessary.
- Minor abrasion of the vagina or perineum with insertion or removal of the study pessary.
- Vaginal bleeding caused by the study pessary.
- Increased vaginal discharge caused by the study pessary.
- Vaginal epithelial erosion (superficial or deep) from using the study pessary.
- Difficulty urinating or leakage of urine caused by the study pessary.
- Difficulty with defecation caused by the study pessary.
- Embarrassment if the study pessary falls out.
- Minor discomfort if the study pessary rotates out of position or if it falls out.
- Inconvenience caused by the inability of the study pessary to support the subject's prolapse.

[figure not shown]
Each of the risks cited above exist for any patient who chooses a pessary for management of their prolapse and are not unique to the study pessary. Though inconvenient, these are not life threatening.

The novelty of our pessary lies in its ability to flex, which we hypothesize will make insertion and removal more comfortable for the subject. Because it does not contain buttons, mechanism, or moving parts, it does not have mechanical features subject to failure. The soft and pliable nature of the molded silicone should not be capable of pinching the vaginal epithelium when the study pessary is elongated for removal, but this metric will be followed.

In common clinical practice, patients often use their pessaries continuously for 3-6 months without removal or medical evaluation. Per our protocol, the Reia pessary is intended to be used for 3 months continuously, and each subject will be evaluated 1-3 weeks after the study pessary is initially placed to assess for the presence of adverse events. Each subject will be a current pessary user, and during the course of the trial they will be monitored more closely than had they continued to use their existing pessary.

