7.3 Analysis group

7.3.1 All subjects who complete visit 0 will be included in the analysis group.

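### SAP section 7 can pool washout events on the current pessary with study-pessary events in one tally, and drops the protocol's comparison between the two devices

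*SAP*

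**What the plan says.** Protocol 4.0 makes adverse events one of two primary endpoints and words it as a comparison: "Prevalence and severity of adverse events that subjects experience using the study pessary compared to those experienced with their current pessary". The time frame is Weeks 0 to 16, with the explanation "Adverse events can occur with use of the current pessary or during the treatment phase with the study pessary". The event types listed there include some unrelated to the pessary or to a study visit.

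SAP 7.1.1 keeps only the first half of that endpoint: events, as defined later in the section, "that subjects experience using the study pessary". SAP 7.2.6 builds the data set from five items. Four cover subjective reports and exam findings that are related to the study pessary and are either new or worse than baseline on the current pessary. The fifth is "Any additional entries in the F-3010 Trial Adverse Event Log". Under 7.2.4, staff may log events of the kinds already described as well as anything not otherwise captured. Under 7.3.1, "All subjects who complete visit 0 will be included in the analysis group". SAP 7.4.1 counts the resulting events by severity and by type. Success under 7.5.1 is the absence of serious, related events that could endanger the general population.

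On exam findings, protocol 4.0 lists "vaginal irritation, vaginal ecchymosis, vaginal abrasions/superficial cuts, vaginal erosion, vaginal bleeding, vaginal discharge, or urinary retention", and protocol 14.0 names as a risk "Vaginal epithelial erosion (superficial or deep) from using the study pessary". The SAP 7.2.2 list opens with perineal tearing, irritation and ecchymosis and continues "vaginal abrasions/superficial cuts, deep vaginal erosion, vaginal bleeding, granulation tissue, and copious vaginal discharge". Urinary retention is not on it.

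**The concern.** The tally in 7.4.1 is the only planned analysis of a primary safety endpoint. If its data set mixes events on two devices, a reader cannot tell how many belong to the device under study. The unfiltered fifth item also makes inclusion depend on whether site staff chose to make a log entry: an event that fails the first four items can come back through the log.

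The protocol's own question is how the study pessary compares with the pessary each woman already uses. The SAP has no count for the current pessary to set beside the study-pessary count. Items one to four use the current pessary only as a filter. A problem that was present at baseline and resolved on the study pessary is therefore never counted, while a problem that appeared or worsened is.

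The exam list is a lesser matter. If superficial erosion has no category of its own, it may be filed under another finding or not counted at all.

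**Working it through.** The plan states no expected event rate and no test for this endpoint, so there is no figure to reproduce. The check is a comparison of texts, with arithmetic on the visit windows to show scale.

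**1. Trace one case.** Protocol 13.0 withdraws a woman who stops tolerating her current pessary during washout. Suppose the site logs her event.
- SAP 7.2.6, items one to four: not admitted, because the event is not related to the study pessary.
- SAP 7.2.6, item five: admitted, because it is a log entry and no condition is attached.
- SAP 7.3.1: she is in the analysis group, because she completed Visit 0.
- SAP 7.4.1: counted by severity and type, with no split by device, period or relatedness.

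Her event enters the data set for an endpoint that 7.1.1 defines by use of the study pessary, although she never had one.

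**2. Compare with the protocol, element by element.**
- Washout events: inside the protocol endpoint as the comparator; in the SAP they can enter only through the log, and then in the same tally.
- Unrelated events: inside the protocol endpoint; in the SAP excluded by items one to four and admitted by item five. This conflict is internal to the SAP.
- Comparison with the current pessary: stated in the protocol; absent from SAP 7.1.1 and 7.4.1.

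**3. Scale.** Protocol 6.0 places Visit 1 at w = 3 to 5 weeks after Visit 0, and Visit 3 at t = 11 to 13 weeks after Visit 1. The washout share of observation time is w/(w + t):
- lowest: 3/(3 + 13) = 3/16 = 18.8%
- nominal: 4/(4 + 12) = 4/16 = 25.0%
- highest: 5/(5 + 11) = 5/16 = 31.3%

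These are shares of time. They would be shares of log entries only if entries arose at a constant rate, and even then not shares of the tally, which also holds events from items one to four.

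The same windows show why a side-by-side report must state observation time. The ratio t/w runs from 11/5 = 2.2 to 13/3 = 4.3, with 12/4 = 3 at the nominal lengths. At equal event rates, the treatment phase would therefore show about two to four times as many events as the washout.

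**4. Exam list.** The protocol names erosion without a depth limit in 4.0 and at both depths in 14.0; SAP 7.2.2 names deep erosion only. Protocol 10.0 excludes women with deep erosion found when the current pessary is removed, but not those with superficial erosion. Eligible women may therefore have superficial erosion at baseline, and the third and fourth items of 7.2.6 need that baseline to tell a new finding from a worsened one. Protocol 4.0 lists urinary retention among exam findings, and protocol 6.0 has it assessed at the Visit 0 and Visit 2 exams. In the SAP the nearest item is obstructed urination, reported by the subject (7.2.1).

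**The case against.** A reader might infer that the SAP brings in events foreign to the protocol's endpoint. The documents do not support that. Protocol 4.0 covers Weeks 0 to 16, use of the current pessary, and unrelated events. The departure is that washout events can be pooled when they should serve as the comparator, and that the comparison itself has gone.

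It can also be said that the SAP never states outright that washout entries are counted, that 7.1.1 defers to the definitions below it, and that log F-3010, which is not among the documents, may record onset, device and relatedness. All of that is true. But 7.2.6 and 7.4.1 use none of those fields, so even a complete log would not keep the events apart under the plan as written.

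The constant-rate reading of the 19% to 31% has no support. Women enter washout on a pessary used for more than 3 months, whereas treatment starts with a new device.

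Nor does the pooled tally decide success. SAP 7.5.1 looks only at serious and related events, so unrelated entries cannot change it. What remains is that 7.5.1 does not say related to which device.

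On the exam list, it is tempting to conclude that superficial erosions and retention will be missed. That is not shown. SAP 15.1 has data collected under the protocol, whose exams look for erosions of any depth; protocol 17.0 has all adverse events recorded and itself lists retention among subject-reported events; SAP 7.2.1 collects obstructed urination; and a superficial lesion may be recorded as an abrasion or in the log. The mismatch in the lists stands, but loss of cases is only possible.

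**Conclusion.** Wrong as written, and worth correcting, though short of a defect that must be fixed before the trial can be interpreted at all. SAP section 7 delivers neither its own endpoint, because the fifth item of 7.2.6 undoes the filter in the first four, nor the protocol's, because the comparison with the current pessary is missing. Current-pessary events from the washout can be counted with study-pessary events, including events in women who never received the study pessary.

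The number of events affected cannot be stated: the documents give no event rates and no count of women who leave before fitting. The washout's share of observation time, about 19% to 31%, rests only on the planned visit windows and indicates scale. The consequence falls on the descriptive tally. The success criterion is exposed only through its silence on which device a related event must be related to. The narrower exam list is a secondary inconsistency.

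**What to change.** - **SAP 7.2.6 and 7.4.1:** assign every event, log entries included, to the device in use at onset and to related or unrelated.
- **SAP 7.3.1 and 7.4.1:** tally three sets separately: study-pessary events, with onset at or after the first insertion attempt, among women in whom insertion was attempted; current-pessary events in the washout, among all who complete Visit 0; and unrelated events. Keeping the Visit 0 group for the second set ensures that events in women who were never fitted are still reported.
- **SAP 7.1.1 and 7.4.1:** restore the protocol's comparison by reporting the two periods side by side, each with its number of women and its observation time.
- **SAP 7.5.1:** state that related means related to the study pessary.
- **SAP 7.2.2:** align the exam list with the protocol by recording vaginal erosion by depth and adding urinary retention. Make the same change on form CP-002-03 if it carries the SAP's list.

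The cost is a few lines of SAP text and possibly a small form change. Each log entry will need an onset date and a relatedness judgement; if F-3010 does not already hold these, sites will have to supply them.
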